## **9.2 Termination or Suspension of the Trial**

MC2 reserves the right to terminate or suspend the trial at any time. In case of premature termination or suspension of the trial, the contract research organization (CRO) project manager will promptly inform the investigators, regulatory authorities, and IRBs about the premature termination or suspension, including the reason for it. In terminating the trial, MC2 and the investigator will ensure that adequate consideration is given to the protection of the subjects' interests.

# **10.0 DATA HANDLING AND RECORD KEEPING**

## **10.1 Recording of Data**

### **10.1.1 Source documents**

Source data are all the information in original records and copies of original records of clinical findings, observations, or other activities in the trial, which are necessary for the reconstruction and evaluation of the trial. The identification of any data to be recorded directly on the eCRFs is to be considered source data.

Trial data collection procedures must ensure that each data element can be traced with a high level of confidence from its originator or recorder to its representation in the trial database and then to its place in the analysis and report of trial results. Once recorded, the trial data must be protected from unauthorised modification or deletion, and all authorised modifications and deletions must be securely linked in the permanent record with their author, time of change, and reason for change (i.e., the audit trail must be maintained).

The investigator will permit trial-related monitoring, audit(s), IRB/IEC review(s) and regulatory inspection(s), with direct access to all the required source records.

The principal investigator will certify the data to be accurate and complete and will release the data for transmittal to MC2 or designee.

Source records need to be preserved for the maximum period of time permitted by local requirements (see [Section 10.2](#)). For each subject enrolled, the investigator will indicate in the source record(s) that the subject participated in the trial.

### **10.1.2 Case report forms**

The primary data collection tool for the trial is an eCRF designed specifically for the trial. For each subject enrolled in the trial, an eCRF will be completed by the trial coordinator and signed by the investigator or his/her designate.

The investigator will be responsible for ensuring the accuracy of all data entered in the eCRFs. All eCRFs are to be completed in a timely manner.

Errors occurring in the eCRFs will be queried. Queries raised by data reviewers must be addressed by site personnel.

On request, the investigator will provide the MC2 with additional data relating to the trial, or copies of relevant source records, duly anonymised (i.e., subject's name is redacted).

## **10.2 Retention of Documents**

The investigator shall take responsibility for maintaining adequate and accurate source documents of all observations and data generated during this trial, including any data clarification forms received from the MC2 or designee. Such documentation is subject to inspection by the sponsor or its agents, the FDA and/or other regulatory agencies. The investigator is responsible for retention of essential documents including the Investigator Trial File until MC2 informs the investigator that the documents are no longer to be retained or longer if required by local regulations.

# **11.0 QUALITY CONTROL AND QUALITY ASSURANCE**

## **11.1 Direct Access to Source Documents**

As specified in the investigator's agreement, the investigator agrees to allow trial-related monitoring, audit(s), IRB/IEC review(s) and regulatory inspection(s), with direct access to all the required source records, and to allocate his/her time and the time of his/her staff to the auditor/inspector to discuss findings and any issues.

## **11.2 Monitoring Procedures**

The Clinical Trial Monitor will contact and/or visit the investigator site periodically to verify the adherence to the protocol, the maintenance of trial-related source records, and the completeness and accuracy of all eCRF entries compared to source data. The investigator will cooperate with the trial monitor to ensure that any discrepancies that may be identified are resolved.

## **11.3 Audit and Inspection**

The investigator will make all the trial-related source data and records available to a quality assurance auditor mandated by the sponsor, or to domestic or foreign regulatory inspectors, after reasonable notice. The main purposes of an audit or inspection are to confirm that the rights and well-being of the subjects have been adequately protected, and that all data relevant for the evaluation of the IP have been processed and reported in compliance with GCP/ICH and applicable regulatory requirements.

The investigator is to notify the MC2 or designee immediately of any inspection by regulatory authorities or IRBs.

## **12.0 ETHICS**

### **12.1 Ethical Conduct of the Trial**

This trial must be carried out in compliance with the protocol and the applicable laws and regulatory requirements of the appropriate regulatory agency. The trial must be conducted in accordance with the ethical principles originating from the Declaration of Helsinki and amendments and the ICH-GCP guidelines.

### **12.2 Institutional Review Board (IRB) or Independent Ethics Committee (IEC)**

This protocol, the proposed informed consent form, and other information for subjects must be reviewed and approved by an IRB or IEC, before the start of the trial, in compliance with local regulations. This committee must also approve any amendments to the protocol, other than administrative ones, before initiation of the amendment procedures.

### **12.3 Subject Information and Consent**

Before participation in the trial, each subject or guardian is required to provide written consent to participate in the trial. No trial-specific procedures will be performed before a subject's informed consent is obtained.

### **12.4 Disclosure and Confidentiality**

#### **12.4.1 Confidentiality of trial documentation**

By signing the protocol, the investigator agrees to keep all information provided by the sponsor in strict confidence and to request similar confidentiality from his/her staff and the IRB or IEC. Trial documents provided by the trial sponsor (i.e., protocols, Investigators' Brochures, eCRFs and other material) will be stored appropriately to ensure their confidentiality. The information provided by the sponsor to the investigator may not be disclosed to others without direct written authorisation from the sponsor, except to the extent necessary to obtain informed consent from subjects who wish to participate in the trial.

#### **12.4.2 Privacy of individual health information**

The investigator will undertake to protect the privacy of all individually identifiable health information except as specifically authorised by each individual subject through the written informed consent. The Informed Consent document will include a request of the subject's consent to release the collected data for research purposes in such a way that the individual's identity remains masked. While all data records will be identified by the corresponding subject number, the identity of the subject will be held in confidential source documents at the trial site. All trial personnel with access to this information are legally bound not to disclose such information.

## 13.0 EMERGENCY PROCEDURES

### 13.1 Emergency Unblinding (Not Applicable)

This is an open-label trial.

#### 13.2.2 Reporting procedures

##### Serious adverse events

For each SAE, the investigator will complete a Serious Adverse Event Report Form and assess the relationship of each SAE to trial treatment. The completed form(s) should be sent electronically to the UBC using the SAE Reporting fax number within 24 hours of first knowledge of the SAE.

Follow-up reports regarding the status of the SAE and the subject's subsequent course should be submitted until the SAE has subsided, the condition stabilised (in the case of persistent impairment), the subject receives alternative therapy, or the subject dies. The form and fax confirmation will be retained. Contacts for reporting SAEs, pregnancies and other safety concerns are provided to each site.

## 14.0 INSURANCE

MC2 has taken out appropriate insurance policies covering the subjects in the clinical trial in accordance with applicable laws and regulations.

## 15.0 PUBLICATION POLICY

The clinical trial information will be posted on [www.clinicaltrials.gov](http://www.clinicaltrials.gov) and in accordance with applicable regulations.

All publications (e.g., manuscripts, abstracts, oral/slide presentations, book chapters) based on this trial must be submitted to MC2 for review, as specified in the Clinical Trial Agreement between the institution, investigator and MC2 or its designee.

### List of Abbreviations and Definitions of Terms

Abbreviation	Definition
ACTH	Adrenocorticotropic hormone
AE	Adverse event
ALP	Alkaline phosphatase
AUC 0-7	Area under the time-concentration curve from time zero to 7 hours
AUC 0-t	Area under the time-concentration curve from time zero to the last measurable concentration
AUC 0-∞	Area under the time-concentration curve from time zero to infinity
BDP	Betamethasone dipropionate
BSA	Body surface area
CAL	Calcipotriene (United States term) / Calcipotriol (European Union term)
C max	Maximum plasma drug concentration
CRO	Contract Research Organisation
ECG	Electrocardiogram
eCRF	Electronic case report form
FDA	Food and Drug Administration
HPA	Hypothalamic-pituitary-adrenal
ICF	Informed consent form
IP	Investigational product
IRB	Institutional Review Board
IWR	Interactive web response
MCV	Mean corpuscular volume
MedDRA	Medical Dictionary for Regulatory Activities
OTC	Over the counter
PGA	Physician's Global Assessment
PK	Pharmacokinetics
PTH	Parathyroid hormone
RBC	Red blood cell
SAE	Serious adverse event
SD	Standard deviation
SOP	Standard operating procedure
T 1/2	Elimination half-life
T max	Time to maximum plasma drug concentration
UPT	Urine pregnancy test
US	United States
WBC	White blood cell

## 1. INTRODUCTION

This Statistical Analysis Plan (SAP) is based on the study Protocol version 3.0 dated December 20, 2017.

This document provides additional details concerning the statistical analyses outlined in the protocol and reflects any changes to the protocol from any amendments. This plan will not repeat all the definitions given in the protocol but will provide further details of the summaries and analyses planned therein.

## 2. STUDY OBJECTIVES

The primary objective is to evaluate the pharmacokinetic profile of the active ingredients and their main metabolites after application of MC2-01 cream, and compare with the active comparator following once daily topical application under maximum-use conditions in subjects with extensive psoriasis vulgaris.

The secondary objective is to evaluate the effect of MC2-01 cream on the hypothalamic-pituitary-adrenal (HPA) axis and calcium metabolism following once daily topical application under maximum-use conditions in subjects with extensive psoriasis vulgaris.

[figure not shown]
## 3. STUDY DESIGN

This is a Phase 2, randomised, open-label, parallel-group, multicentre trial in which the investigational product, MC2-01 cream, and CAL/BDP ointment (comparator) are investigated in subjects with clinically diagnosed extensive psoriasis vulgaris of disease severity assessed by Physician's Global Assessment (PGA) of at least moderate (Figure 1). Subjects who meet inclusion/exclusion criteria will be randomly assigned in a 1:1 ratio to receive either MC2-01 cream or the comparator. Subjects assigned to MC2-01 cream will apply 1 dose of trial medication topically once daily for 8 weeks and the subjects assigned to the comparator will apply 1 dose of trial medication topically once daily for 4 weeks.

At Week 4, the pharmacokinetic (PK) profile of calcipotriene (CAL), betamethasone dipropionate (BDP) and their main metabolites MC1080 and betamethasone 17-propionate, respectively, will be assessed for both treatment groups. At Week 8, the PK profile of CAL, BDP and their main metabolites will be assessed for the MC2-01 cream treatment group only. At Week 4 and Week 8, the effect of once-daily use of MC2-01 cream on the HPA axis and calcium metabolism will be evaluated for MC2-01 cream treatment group. Other safety assessments (local skin reactions, AEs, laboratory tests, electrocardiogram (ECG)), vital signs and physical examinations) and efficacy assessments are also performed.

[figure not shown]
### Figure 1: Study Design

#### Trial Design for Subjects Assigned to the MC2-01 Cream

\*Follow-up visits will be required only for subjects who have unresolved AEs or whose calcium levels have not returned to pre-treatment levels at the End of Treatment visit.

#### Trial Design for Subjects Assigned to the Active Comparator

\*Follow-up visits will be required only for subjects who have unresolved AEs at the End of Treatment visit.

## 4. HARDWARE AND SOFTWARE

Statistical analysis will be performed following Novella Clinical standard operating procedures (SOP) and on the Novella Clinical computer network. All statistical analysis will be performed using SAS Version 9.3 or higher with program code prepared specifically for the project by qualified Novella Clinical statisticians and SAS programmers.

The SAS programs will generate rich-text-formatted (RTF) output with the “RTF” extension using the SAS Output Delivery System (ODS). The summary tables and listings will be formatted using the Times New Roman 9-point font. The RTF output is included in report documents prepared with Microsoft Word and converted to PDF format without typographical change.

Study data tabulation model (SDTM) data sets and analysis data model (ADaM) data sets will be created and taken as input to validated SAS programs to generate the report-ready tables, listings,

and figures. Each output display will show the names of the data sets and SAS program used to produce it.

## 5. DATABASE CLOSURE

After completion of all data review procedures, validation of the project database, and approval of the data review document by the study sponsor, the clinical database will be closed. Any change to the clinical database after this time will require written authorization, with explanation, by the Sponsor and the Biostatistician.

## 6. SAMPLE SIZE DETERMINATION

The choice of sample size in this trial is not based on statistical considerations, but rather on regulatory considerations with respect to common practice in maximum use studies evaluating pharmacokinetic profiles and evidence of HPA safety. The chosen number of approximately 25 subjects included in the PK population at Week 4 in each treatment arm is considered sufficient to compare the PK properties corresponding to the two treatments.

## 7. HANDLING OF MISSING DATA

No imputation will be made for missing data.

## 8. ANALYSIS POPULATIONS

Three analysis populations will be defined for analysis:

- Safety Population: will include all randomized subjects who have been dispensed the trial medication, excluding subjects who return all of the trial medication unopened. The Safety Population will be used for all safety analyses other than evaluation of the HPA-axis.
- HPA population: will include all subjects in the Safety population that are assigned to MC2-01 cream and who show normal HPA function at Baseline (defined as a 30-minute post-stimulation cortisol level  $\geq 18 \mu\text{g/dL}$ ). Since the objective of the analysis is to estimate the risk to subjects with normal HPA function of HPA-axis suppression following treatment, subjects who meet the definition of HPA-axis suppression at Baseline will be excluded from the analysis. The HPA population will be used for the HPA axis suppression analysis.
- Pharmacokinetic (PK) Population: will include all subjects in the Safety population who have received the planned application of treatment at the Week 4 or Week 8 visit, respectively, and have had at least one post-application blood draw for PK assessment at the corresponding visit. The PK Population will be used for the PK analysis.

---

All safety, HPA and PK analyses will be conducted according to the treatment actually received.

## 9. DATA CONVENTIONS FOR ANALYSIS

### 9.1 General Statistical Principles

All statistical processing will be performed using the SAS system (Version 9.3 or higher).

All observed and derived variables (e.g., change from baseline) used in the summaries of analyses will be presented in by-subject listings. Descriptive statistics will be used to provide an overview of the safety and PK results. For categorical parameters, the number and percentage of subjects in each category will be presented. The denominator for percentage will be based on the number of subjects appropriate for the purpose of analysis. For continuous parameters, descriptive statistics will include number of observations, mean, standard deviation (SD), median, and range. The PK parameters will be summarised using appropriate descriptive statistics including median, lower and upper quartiles, minimum and maximum. Geometric means and coefficient of variation (CV) will be provided as appropriate.

It is planned that the data from all centers that participate in this protocol will be combined so that an adequate number of subjects will be available for analysis.

No interim analyses are planned.

### 9.2 Study Day and Baseline

For purpose of the SAP, Day 1 is defined as the date of first application of study drug, which corresponds to Randomization/Visit 1 of the study protocol. Study day is calculated relative to the date of Day 1.

Baseline is defined as the last available measurement prior to first application of study drug. Change from baseline is defined as the post-baseline value minus the baseline value.

## 10. STATISTICAL EVALUATION

### 10.1 Subject Disposition

The number and percentage of subjects who are screened, randomized, included in each analysis population, who complete the study, and withdraw from the study (overall and by reason for withdrawal) will be summarized, overall and by treatment group.

A by-subject enrolment and disposition listing will be presented for all randomized subjects.

### 10.2 Protocol Deviation

Protocol deviations will be presented in a by-subject listing.

### 10.3 Demographic and Baseline Characteristics

Demographics, baseline characteristics will be summarized overall and by treatment for the Safety, HPA and PK populations. The following demographic and baseline variables will be included:

- Age (years)
- Gender
- Race
- Ethnicity
- Fitzpatrick Skin Type
- Weight (kg)
- Height (cm)
- Baseline HPA Axis Suppression Status (MC2-01 cream group only)
- Baseline PGA
- Baseline Total BSA (%)
- Duration of psoriasis in years (calculated as year of baseline minus year of first psoriasis diagnosis)

### 10.4 Study Drug Exposure and Accountability

Subjects will record the date of each trial medication application in the subject diary. The kit number, and corresponding date dispensed and returned will be collected.

The weight of the returned kits will also be collected.

The following parameters of study medication exposure will be summarized by treatment group and by study period, i.e., from day 1 to Week 4 (both groups) and from day 1 to Week 8 (MC2-01 cream group), for the Safety Population:

- Total number of days of exposure to the study drug, defined as the date of last application of study drug during the period minus date of first application plus one. The last application is the in-clinic dosing at Week 4 visit (Day 1 to Week 4 period) and Week 8 visit (Day 1 to Week 8 period).
- Total number of missed doses during each study period per subject diary
- Total number of applications during each study period, defined as the total number of doses required minus total number of doses missed. Total number of required doses is defined as total number of days of exposure minus any days of investigator approved stop (if applicable)
- Total weight of trial medication used (g) during each study period, defined as the summation of amount of drug used for all dispensed kits. Amount of drug used per kit is defined as the difference in weight between the returned and dispensed kits, where weight

of dispensed kits is a unit value. Amount of drug used for sealed and unreturned kits will be assumed to be 0.0 g

- Amount of drug used per week (g/per week), defined as the total amount of drug used divided by total number of days of exposure to the study drug multiplied by 7

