Trial Design:	
This is a Phase 2, randomised, open-label, parallel-group, multicentre trial in which the investigational product, MC2-01 cream, and calcipotriene/betamethasone ointment (comparator) is investigated in subjects with clinically diagnosed extensive psoriasis vulgaris.
 
After having provided informed consent, the subjects will undergo screening procedure. Subjects that fulfil the inclusion and exclusion criteria are randomly assigned in a 1:1 ratio to receive the MC2-01 cream or the comparator.
 
Subjects assigned to the MC2-01 cream will be treated once-daily for 8 weeks and the subjects assigned to the comparator will be treated once-daily for 4 weeks.
 
At Week 4, the pharmacokinetic (PK) profile of calcipotriene (CAL), betamethasone dipropionate (BDP) and their main metabolites MC1080 and betamethasone 17-propionate, respectively, will be assessed for both treatment groups. At Week 8, the PK profile of calcipotriene, betamethasone and their main metabolites will be assessed for the MC2-01 cream treatment group only.
 
The effect of use of MC2-01 cream on the hypothalamus-pituitary-adrenal (HPA) axis and calcium metabolism will be evaluated at week 4 and week 8.
 
The maximum trial duration for each subject will be approximately 12 or 16 weeks and includes a screening period of up to 4 weeks (if washout of medication is required), a treatment period of 4 or 8 weeks, and a follow-up period of up to 4 weeks (if required for follow-up of adverse events, calcium concentrations, and/or HPA axis suppression).

Sample Size:	
It is planned to enrol approximately 60 subjects with the aim to have 25 subjects included in the PK population after 4 weeks of treatment in each treatment arm.
 
The choice of sample size in this trial is not based on statistical considerations, but rather on regulatory considerations with respect to common practice in maximum use studies evaluating pharmacokinetic profiles and evidence of HPA safety

Trial Population:	Generally healthy males or non-pregnant females, at least 18 years of age, with a clinical diagnosis of plaque psoriasis (psoriasis vulgaris) of at least 6 months duration, with a Physician Global Assessment (PGA) of disease severity of at least moderate on the trunk, limbs and/or scalp and a treatment area between 20% and 30% of the BSA, excluding psoriatic lesions on the face, genitals, and intertriginous areas.

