## 6.8 Treatment Compliance

Records of trial product used and dosages administered will be kept during the trial. The trial monitor will note product accountability during site visits and at the completion of the trial.

At all on-treatment visits, the subject will be asked if he/she has used the medication as prescribed. If this is not the case, the degree and nature of noncompliance will be specified. In addition, subjects will be asked to complete a dosing diary during the treatment period as a measure of treatment compliance. Subjects who are consistently noncompliant will be counseled.

Subjects will be asked to return all used and unused tubes in the outer box at each visit. All returned tubes that had been dispensed to a subject and have broken seals will be weighed to determine the amount of the investigational product used per treatment phase.

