[2] Total number of doses applied= total number of doses required – total number of missed doses. Total number of doses required = total number of days of exposure – any days of investigator approved stop.

Table 14.1.3: Summary of Extent of Exposure and Compliance  
Safety Population

	Day 1 to Week 8	Day 1 to Week 4	
	MC2-01 Cream (N=XX)	MC2-01 Cream (N=XX)	Active Comparator (N=XX)
Total Amount of Drug Used (g)[3]			
N	XX	XX	XX
Mean (SD)	XX.X (XX.X)	XX.X (XX.X)	XX.X (XX.X)
Median	XX.X	XX.X	XX.X
Q1, Q3	XX, XX	XX, XX	XX, XX
Minimum, Maximum	XX, XX	XX, XX	XX, XX
Amount of Drug Used per Week (g/per week)[4]			
N	XX	XX	XX
Mean (SD)	XX.X (XX.X)	XX.X (XX.X)	XX.X (XX.X)
Median	XX.X	XX.X	XX.X
Q1, Q3	XX, XX	XX, XX	XX, XX
Minimum, Maximum	XX, XX	XX, XX	XX, XX

[3] Total amount of drug used (g) is defined as the summation of amount of drug used per kit for all returned kits. Amount of drug used per kit is the difference in weight between the returned and dispensed kits. Amount of drug used for sealed and unreturned kits will be assumed to be 0.0 g.

[4] Amount of drug used per week (g/per week) is defined as the total amount of drug used divided by total number of days of exposure to the study drug multiplied by 7.

Generated on XX/XX/XX:XXXX by SMYDM / Uses: XXXX / Reference: Data Listing XXXX

Table 14.1.4: Summary of Concomitant Medications  
by Anatomical Therapeutic Chemical Class (ATC) and Preferred Term  
Safety Population

	MC2-01 Cream (N=XX)	Active Comparator (N=XX)
Subjects with any Concomitant Medication, n (%)	XX (XX.X)	XX (XX.X)
<< Anatomical Therapeutic Chemical Class >>		
<< Medication Preferred Term >>	XXXXX	XXXXX
<< Medication Preferred Term >>	XXXXX	XXXXX
<< Medication Preferred Term >>	XXXXX	XXXXX
<< Anatomical Therapeutic Chemical Class >>		
<< Medication Preferred Term >>	XXXXX	XXXXX
<< Medication Preferred Term >>	XXXXX	XXXXX
<< Medication Preferred Term >>	XXXXX	XXXXX

Note: Any medication ongoing or with stop date on or after Day 1 is a concomitant medication. Counts reflect number of subjects in each treatment group reporting one or more prior medication that map to the WHO Drug anatomical therapeutic chemical or preferred term. A subject may be counted once only in each row of the table.

Generated on XX/XX/XX:XXXX by XXXXX / Uses: XXXX / Reference: Data Listings XXXX

MC2 Therapeutics  
Protocol Number: MC2-01-C3

Page X of Y

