Subject Number	Total Number of Days of Exposure[1]	Total Number of Expected Doses[2]	Total Number of Missed Doses	Total Number of Applied Doses[3]	Total Amount of Drug Used (g)[4]	Amount of Drug Used per week (g/per week)[5]
XX-XXX	XX	XX	XX	XX	XX.X	XX.X
XX-XXX	XX	XX	XX	XX	XX.X	XX.X

[1] Total number of days of exposure to the study drug is defined as the date of last application of study drug minus date of first application plus one. Last application is applied in-clinic at Week 4 visit.

[2] Total number of expected doses is defined as total number of days of exposure minus any days of investigator approved stop (if applicable)

[3] Total number of doses applied, defined as the total number of doses required minus total number of doses missed.

[4] Total amount of drug used (g), defined as the summation of amount of drug used per kit for all dispensed kits.

[5] Amount of drug used per week (g/per week), defined as the total amount of drug used divided by total number of days of exposure to the study drug multiplied by 7.

Generated on XX/XX/XX:XXXX by XXXXX / Uses: XX

MC2 Therapeutics  
Protocol Number: MC2-01-C3

Page X of Y

Data Listing 16.2.5.3.2: Overall Study Drug Exposure and Compliance, Day 1 to Week 8 Period  
All Randomized Subjects  
[MC2-01 Cream]

Subject Number	Total Number of Days of Exposure[1]	Total Number of Expected Doses[2]	Total Number of Missed Doses	Total Number of Applied Doses[3]	Total Amount of Drug Used (g)[4]	Amount of Drug Used per week (g/per week)[5]
XX-XXX	XX	XX	XX	XX	XX.X	XX.X
XX-XXX	XX	XX	XX	XX	XX.X	XX.X

[1] Total number of days of exposure to the study drug is defined as the date of last application of study drug minus date of first application plus one. Last application is applied in-clinic at Week 8 visit.

[2] Total number of expected doses is defined as total number of days of exposure minus any days of investigator approved stop (if applicable)

[3] Total number of doses applied, defined as the total number of doses required minus total number of doses missed.

[4] Total amount of drug used (g), defined as the summation of amount of drug used per kit for all dispensed kits.

[5] Amount of drug used per week (g/per week), defined as the total amount of drug used divided by total number of days of exposure to the study drug multiplied by 7.

Generated on XX/XX/XX:XXXX by XXXXX / Uses: XX

MC2 Therapeutics  
Protocol Number: MC2-01-C3

Page X of Y

Data Listing 16.2.5.4.1: Subject Treatment Diary Card  

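### Opened tubes that are never returned count as 0.0 g used, which biases grams used and grams per week downward for those subjects

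*SAP*

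**What the plan says.** SAP 10.4 (Study Drug Exposure and Accountability) plans total grams and grams per week by treatment group and period in the Safety Population. On the amount used it says: "Amount of drug used per kit is defined as the difference in weight between the returned and dispensed kits". The dispensed weight is a fixed unit value. The rule at issue follows: "Amount of drug used for sealed and unreturned kits will be assumed to be 0.0 g". Footnote 3 of Table 14.1.3 repeats it. Grams per week is "defined as the total amount of drug used divided by total number of days of exposure to the study drug multiplied by 7", so any error in the total carries straight through.

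The wording of the sum varies. SAP 10.4 sums over dispensed kits, as do Data Listings 16.2.5.3.1 and 16.2.5.3.2: "Total amount of drug used (g), defined as the summation of amount of drug used per kit for all dispensed kits". Table 14.1.3 footnote 3 says: "Total amount of drug used (g) is defined as the summation of amount of drug used per kit for all returned kits".

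Protocol 6.8 works with tubes. "Subjects will be asked to return all used and unused tubes in the outer box at each visit", and returned tubes that "have broken seals will be weighed to determine the amount of the investigational product used per treatment phase". The shell of Data Listing 16.2.5.2 records return status, seal and return weight tube by tube, with a third status for redispensed tubes. SAP section 7 says that missing data are not imputed.

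**The concern.** The rule gives one value to two different situations. A tube that comes back sealed was not used, so zero is an observation. A tube that does not come back has no return weight, so its use is missing, and 0.0 g is a fixed value put in place of an unknown amount, at the lowest point of its possible range.

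Both trial objectives are framed as maximum-use conditions. Total grams and grams per week are the only planned summaries of the quantity applied. Days of exposure, missed doses and number of applications are summarised too, but they do not measure amount. If use is understated, a reader of Table 14.1.3 may conclude that subjects fell further short of maximum use than they did, or may miss subjects who went above the 100 g weekly maximum. No count of unreturned tubes and no alternative display is planned, so the table would not show how much of the total rests on the assumption.

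**Working it through.** The documents give no exposure total, so there is no planned figure to reproduce. The check is direct arithmetic from the SAP definitions.

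**Inputs**
- Tube content: 60 g in both arms (protocol 6.5).
- Days of exposure: last application minus first plus one (SAP 10.4). The first application is at Visit 1, which is protocol Day 0. Week 4 is Day 28 ± 2, so 28 − 0 + 1 = 29 days (27 to 31). Week 8 is Day 56 ± 2, so 57 days (55 to 59).
- Grams per week: total / days × 7.
- True use u of a never-returned tube: 0 to 60 g. The rule takes u = 0, so the error in the total is −u.

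**Per subject, one never-returned tube, u = 60 g**

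| Last application | Days | Error in g/week |
|---|---|---|
| Week 4 | 29 | −60/29 × 7 = −14.48 |
| Week 4, window limits | 27; 31 | −15.56; −13.55 |
| Week 8 | 57 | −60/57 × 7 = −7.37 |
| Week 8, window limits | 55; 59 | −7.64; −7.12 |
| Early stop (illustration) | 14 | −60/14 × 7 = −30.00 |

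The window limits hold only for subjects who reach the visit. The Safety Population also contains early discontinuers. The last row takes their own last application as the end of exposure. With u = 30 g every error is halved (−7.24 g/week at 29 days), and with u = 0 there is none.

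**Effect on how the figures read (29 days, one emptied tube not returned)**
- True 90 g/week: 90 × 29/7 = 372.9 g. Reported 372.9 − 60 = 312.9 g, which is 75.5 g/week.
- True 110 g/week: 110 × 29/7 = 455.7 g. Reported 395.7 g, which is 95.5 g/week, below the 100 g maximum.

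**Arm mean (assumption)**
The loss rate is not in the documents. Suppose a share f of an arm each lose one emptied tube and all reach the visit. The mean then falls by f × 14.48 g/week to Week 4 and f × 7.37 g/week to Week 8. For f from 0 to 20% this is 0 to 2.9 and 0 to 1.5 g/week. The protocol synopsis says: "It is planned to enrol approximately 60 subjects with the aim to have 25 subjects included in the PK population". With 1:1 allocation, 60/2 = 30 per arm, so 20% is 6 subjects, and each such tube moves the arm mean by 14.48/30 = 0.48 or 7.37/30 = 0.25 g/week.

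**The case against.** The best defence is that the rule is prespecified, printed under the table and recoverable. Tube-level return status is in Data Listing 16.2.5.2, so a reader could build the bounds. Protocol 6.8 asks for all tubes back at each visit and has the monitor check accountability, so losses may be few. Zero is also conservative for showing that maximum use was achieved, because it cannot inflate grams.

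Part of this stands. The frequency may be low, and the rule is not hidden. But being conservative in one direction does not help in the other: the same zero can bring a subject who exceeded 100 g/week below that line. Having to rebuild the bounds from a listing is also a weak substitute for showing them.

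One could read the phrase as a joint condition, sealed and also unreturned. That does not work, because the seal of a kit that never came back cannot be inspected.

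Two stronger readings are tempting and are not supported:
- *That the plan contains two competing totals, by kit and by tube, 60 g apart for a partly returned kit.* No document states how many tubes a kit holds; two per kit comes only from placeholder rows in a listing shell. The weights recorded are per tube. Counting the missing tube as fully used would require ignoring the SAP's own zero rule for unreturned product. The word kit is loose and worth tidying, but it does not establish a second calculation.
- *That the dispensed and returned wordings give different sums.* While unreturned kits count as zero, the two sums are the same.

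**Conclusion.** The point holds for subjects who opened a tube and never returned it. For them the rule understates total grams by up to 60 g per tube. In grams per week this is up to 14.5 to Week 4 and 7.4 to Week 8 at nominal visit days, and more for early discontinuers. The distortion is larger for single subjects than for arm means, and the arm-mean range rests on an assumed loss rate.

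It would go too far to infer that the reported totals are lower bounds in general. They are unaffected where all opened tubes come back, zero is correct for sealed returns, and the nominal dispensed weight brings an error of its own in either direction. Nor do the documents support a wider effect on the results. The Week 4 PK comparison has treatment group as its only effect, and no planned PK, HPA or calcium analysis uses grams. What is at stake is the descriptive record of how much product was applied.

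**What to change.** In SAP 10.4 and Table 14.1.3 footnote 3:
- Compute use per tube, the unit weighed under protocol 6.8 and recorded in Listing 16.2.5.2, and sum over all dispensed tubes.
- Assign 0.0 g only to tubes returned sealed.
- Report the number of never-returned tubes and of affected subjects by arm and period.
- Show total grams and grams per week with each never-returned tube at 0 g and at 60 g.
- Do not count a redispensed tube as unreturned. How its use is split between the two periods is a separate matter that this change does not settle.
- Align the dispensed and returned wording across text, table and listings. This is editorial now, but the two sums would diverge once unreturned product is no longer fixed at zero.

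The cost is revised wording and a few extra rows in one descriptive table. The tube-level data are already to be listed, and no subject is dropped. The downside is that affected subjects contribute a range instead of a single figure.
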